## **5 ETHICS**

### **5.1 Institutional Review Boards/Independent Ethics Committees**

The protocol, Informed Consent Form (ICF), and appropriate related documents must be reviewed and approved by an Institutional Review Board (IRB) or Independent Ethics Committee (IEC) constituted and functioning in accordance with ICH E6 (Good Clinical Practice, GCP), Section 3, Korea Good Clinical Practice (KGCP), and any local regulations. Any protocol amendment or revision to the ICF will be resubmitted to the IRB/IEC for review and approval.

Documented study approval from the IRB/IEC chairman must be sent to the principal investigator with a copy to the sponsor before study start and the release of any study drug to the site by the sponsor or its designee (ICH E6, Section 4.4). If the IRB/IEC decides to suspend or terminate the study, the investigator will immediately send the notice of study suspension or termination by the IRB/IEC to the sponsor.

Study progress is to be reported to IRB/IECs annually (or as required) by an investigator or sponsor, depending on local regulatory obligations. If an investigator is required to report to the IRB/IEC, he/she will forward a copy to the sponsor at the time of each periodic report. The investigator or the sponsor will submit, depending on local regulations, periodic reports and inform the IRB/IEC of any reportable Adverse Events (AEs) per ICH guidelines and local IRB/IEC standards of practice. Upon completion of the study, the investigator will provide the IRB/IEC with a brief report of the outcome of the study, if required.

In the case of early termination/temporary halt of the study, an investigator should notify the IRB/IEC within the timeline required by each IRB's Standard Operating Procedures (SOP) and a detailed written explanation of the reasons for the termination/halt should be given.

### **5.2 Ethical Conduct of the Study**

This study will be conducted in accordance with standard operating procedures of the sponsor (or designee), which are designed to ensure adherence to GCP guidelines as required by the following:

- Principles of the World Medical Association Declaration of Helsinki 2013
- ICH E6 Guideline for GCP
- KGCP

### **5.3 Subject Information and Informed Consent**

As part of administering the informed consent document, the investigators must explain to each subject or legally acceptable representative, the nature of the study, its purpose, the procedures involved, the expected duration, the potential risks and benefits involved, any potential discomfort, potential alternative procedure or course of treatment available to the subject, and

the extent of maintaining confidentiality of the subject's records. Each subject must be informed that participation in the study is voluntary, that he/she may withdraw from the study at any time, and that withdrawal of consent will not affect his/her subsequent medical treatment or relationship with the treating investigator.

This informed consent should be given by means of a standard written statement, written in nontechnical language. The subject or the subject's legally acceptable representative should understand the statement before signing and dating it and will be given a copy of the signed document. If a subject is unable to read or if a legally acceptable representative is unable to read, an impartial witness should be present during the entire informed consent discussion.

After the ICF and any other written information to be provided to subjects is read and explained to the subject or the subject's legally acceptable representative, and after the subject or the subject's legally acceptable representative has orally consented to the subject's participation in the study and, if capable of doing so, has signed and personally dated the ICF, the witness should sign and personally date the consent form. The subject will be asked to sign an ICF at Visit 1 (Screening) before any study-specific procedures are performed. No subject can enter the study before his/her informed consent has been obtained.

Each subject must sign an approved ICF before study participation. The form must be signed and dated by the appropriate parties. The original, signed ICF for each subject will be verified by the sponsor or sponsor's representative and kept on file according to local procedures at the site.

The subject or the subject's legally acceptable representative should be informed in a timely manner if new information becomes available that may be relevant to the subject's willingness to continue participation in the study. The communication of this information should be documented.

## 6 INVESTIGATORS AND STUDY PERSONNEL

This study will be conducted by qualified investigators under the sponsorship of Eisai Korea Inc. at approximately 20 investigational sites in South Korea.

The name and telephone and fax numbers of contact personnel at the sponsor and of the Contract Research Organization (CRO) are listed in the Investigator Study File (ISF) provided to each site.

## 7 INTRODUCTION

### 7.1 Compound Overview

Levodopa is one of the effective treatments for motor symptoms of Parkinson's Disease. Long-term and high doses of levodopa treatment increase the wearing-off and dyskinesia. Parkinson's Disease patients often need add-on therapy to improve motor fluctuations without dyskinesia to reduce motor and functional disability. Wearing-off is usually improved by dopamine agonist, Monoamine Oxidase-B (MAO-B) inhibitor, and Catechol O-methyltransferase (COMT) inhibitors administered together with dopamine precursor, levodopa.

Safinamide mesilate is a novel oral therapy in the treatment of Parkinson's Disease as an adjunct to levodopa. Mechanism of action of safinamide mesilate includes inhibition of MAO-B, sodium (Nai) channel blockade, and modulation of stimulated release of glutamate. By inhibiting the metabolism of dopamine, Safinamide mesilate enhances endogenous residual dopamine and subsequently increases dopaminergic activity in the brain.

### 7.2 Clinical Experience

Clinical trials with safinamide mesilate, which were 24-week, phase III, double-blind, parallel-group, randomized, multi-center, and multinational trials, demonstrated efficacy and safety in Parkinson's Disease patients with mid-to-late stage experiencing motor fluctuations (NCT01187966 and NCT 00627640). According to approved Food and Drug Administration (FDA) label, most common adverse reactions associated with safinamide mesilate treatment in which the incidence for Safinamide mesilate 100 mg/day was at least 2% greater than the incidence for placebo were dyskinesia, fall, nausea, and insomnia (Table 1).

**Table 1. Incidence of patients with adverse reaction in the safinamide mesilate 50mg/day and 100 mg/day groups compared to placebo in clinical trials**

	Safinamide mesilate 50 mg/day (N=223)	Safinamide mesilate 100 mg/day (N=498)	Placebo (N=497)
Adverse reaction	(%)	(%)	(%)
Dyskinesia	21	17	9
Fall	4	6	4
Nausea	3	6	4

	Safinamide mesilate 50 mg/day (N=223)	Safinamide mesilate 100 mg/day (N=498)	Placebo (N=497)
Adverse reaction	(%)	(%)	(%)
Insomnia	1	4	2
Orthostatic hypotension	2	2	1
Anxiety	2	2	1
Cough	2	2	1
Dyspepsia	0	2	1

In addition, phase II/III clinical trials in Japan indicated the efficacy and safety of safinamide mesilate as add-on therapy to levodopa in Parkinson's Disease patients. In this clinical trial, the most common AEs were nasopharyngitis, dyskinesia, and fall. Among these, the most common adverse drug reaction were dyskinesia and visual hallucinations (Table 2).

**Table 2. Incidence of patients with AEs and adverse drug reaction**

	Adverse events			Adverse drug reaction		
	Placebo (N=141)	Safinamide mesilate		Placebo (N=141)	Safinamide mesilate	
		50 mg/day (N=133)	100 mg/day (N=132)		50 mg/day (N=133)	100 mg/day (N=132)
Nasopharyngitis	11.3	6.8	12.9	-	-	-
Dyskinesia	2.1	8.3	10.6	2.1	8.3	10.6
Fall	5.0	5.3	6.8	2.1	1.5	0.8
Contusion	2.8	3.0	5.3	-	-	-
Visual hallucinations	1.4	3.0	4.5	1.4	3.0	4.5
Back pain	3.5	0.8	3.8	-	-	-
Nausea	0.7	3.0	3.0	0.7	2.3	2.3
Conjunctivitis	0.7	-	3.0	-	-	-
Excoriation	-	-	3.0	-	-	-
Headache	0.7	3.8	1.5	-	2.3	1.5

## 7.3 Study Rationale

Safinamide mesilate was approved by the U.S. Food and Drug Administration (FDA) in March 2017 based on phase III clinical trials (NCT01187966 and NCT 00627640) as adjunctive treatment to levodopa in patients with Parkinson’s Disease experiencing off episodes. In addition, safinamide mesilate was approved by the Ministry of Food and Drug Safety (MFDS) in June 2020 as adjunctive therapy with levodopa-containing products in patients with end of dose motor fluctuations. Previous studies demonstrated that adjunctive therapy of safinamide mesilate to levodopa improves Parkinson’s Disease symptoms and “off” time.

The National Institute for Health and Care Excellence (NICE) guideline 2017 regarding managing symptoms of Parkinson’s Disease recommends only to add adjuvant therapy to a levodopa regimen, under specialist advice. Subjects with various daily doses of levodopa from 315 mg to 1,273 mg per day were included even in the global phase 3 clinical SETTLE study, so there is no clear agreement on the optimal adjuvant therapy compared to the dose.

Furthermore, only limited number of centers and patients from South Korea participated in previous global studies that evaluated the efficacy and safety of safinamide mesilate as an add-on therapy in Parkinson’s Disease patients; only 27 Parkinson’s Disease patients from 4 centers in South Korea had experienced safinamide mesilate as add-on therapy to stable dose of levodopa. In this situation, to assess the efficacy and safety of safinamide mesilate according to the daily dose of levodopa is needed for Parkinson’s Disease patients who need combination therapy with levodopa in South Korea.

## 8 STUDY OBJECTIVES

### 8.1 Primary Objective

To evaluate the change at the 18th week from baseline in daily “off” time measured by subject diary and Parkinson’s Disease Questionnaire-39 (PDQ-39) in patients with Parkinson’s Disease who are receiving levodopa.

### 8.2 Secondary Objective

- To evaluate the change at the 18th week from baseline in below assessments:
  - Movement Disorder Society-Unified Parkinson’s Disease Rating (MDS-UPDRS) Part 3
  - Movement Disorder Society-Unified Parkinson’s Disease Rating (MDS-UPDRS) Part 4
  - King’s Parkinson’s disease Pain Scale (KPPS)
  - Mini-Mental State Examination (MMSE)
- To evaluate the safety of safinamide mesilate in Parkinson’s Disease patients who are receiving levodopa

- To evaluate the change at the 18th week from baseline in daily “on” time without dyskinesia in patients with Parkinson’s Disease who are receiving levodopa

[figure not shown]
## 9 INVESTIGATIONAL PLAN

### 9.1 Overall Study Design and Plan

This is a multi-center, open-label, single-arm, interventional study in Parkinson's Disease patients who are receiving levodopa. Approximately 199 patients will be enrolled and will receive safinamide mesilate (hereinafter, study drug) for approximately 18 weeks (Figure 1).

This study consists of a Screening Period, Baseline Period, Treatment Period, and Taper Period. The investigators will obtain informed consent at Visit 1 (Screening Visit). Subjects who are eligible for this study can enter the study. During the Screening Period, if subjects have previously taken medication such as COMT inhibitor and/or MAO-B inhibitor, they have to undergo an appropriate wash-out period for each medication before conducting Visit 2 (Baseline). During the Treatment Period, subjects will take the study drug daily for 18 weeks, and scheduled study visits will be Visit 3 and Visit 4 (18 weeks: EOT).

Subjects will complete their participation in the clinical trial after they complete Visit 4 (EOT). For subjects who require tapering at the time of Visit 4 (EOT), they will enter a Taper Period for 1 week. The Taper Period may be omitted if the subject's daily dose of the study drug at the end of treatment is 50mg, if subjects will continue to take the study drug after the completion of the trial, or if it is considered not required by an investigator.

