### **9.1.1 Screening Period**

The purpose of the Screening Period is to obtain informed consent and to establish protocol eligibility. Informed consent will be obtained after the study has been fully explained to each subject and before the conduct of any screening procedures or assessments. Procedures to be followed when obtaining informed consent are detailed in Section 5.3.

Subjects must have a diagnosis of Parkinson's Disease and receive levodopa at a stable dose for at least 4 weeks prior to the screening visit. After signed informed consent is obtained from the subject or for subjects from Legally Acceptable Representatives (LARs), a medical history interview, identification of prior and concomitant medications, identification of concomitant therapies, height, weight, physical examination, urine pregnancy test (females of childbearing potential only), 12-lead electrocardiogram (ECG; if deemed necessary by an investigator), vital signs, clinical laboratory tests (hematology, chemistry, and urinalysis), and Adverse Events (AE) assessment will be conducted for evaluation of eligibility criteria, and will include confirmation that the subject meets diagnostic criteria for Parkinson's Disease.

At Visit 1 (Screening), subjects will perform the Mini-Mental State Examination (MMSE) among the efficacy assessments. Also, a diary will be handed out to subjects and/or their caregivers, and investigator will train them how to complete the diary. Subjects who meet the eligibility criteria of the study will be instructed to complete the diary for 3 consecutive days prior to Visit 2 (Baseline).

If subjects have previously taken medication such as COMT inhibitor and/or MAO-B inhibitor, they have to undergo an appropriate wash-out period for each medication (3 days for COMT inhibitor; 14 days for MAO-B inhibitor).

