### 9.1.3 Treatment Period

Subjects whose screening assessments including the wash-out period and evaluations are completed and reviewed by the investigators and who continue to meet all of the inclusion/exclusion criteria will enter the Treatment Period. Subjects will take the study drug every day for 18 weeks.

The dose of the study drug is 50 mg once a day for 2 weeks (14 days) starting from the next day after Visit 2 (Baseline), and 100 mg once a day afterwards. Subjects who need to increase the dose at the discretion of an investigator shall visit the site (unscheduled) prior to the dose increase.

Subjects whose dose cannot be increased to 100 mg/day within 4 weeks following Visit 2 (Baseline) will be dropped out from the clinical trial.

If Adverse Events (AE) occur in subjects who have increased the dose, the dose may be reduced back to 50 mg/day at the discretion of an investigator through unscheduled site visit or phone visit. After reduction from 100mg/day to 50mg/day, the dose may be increased back to 100 mg/day at the discretion of an investigator.

Subjects will return to the site at 8 weeks and 18 weeks for Visit 3 and Visit 4 (EOT), respectively. The “windows” permitted for Visit 3 (8 weeks) will be -4 weeks and +2 weeks; for Visit 4 (18 weeks: EOT) will be +/- 2 weeks. Safety assessments including AE assessment, 12-lead ECG (if deemed necessary by an investigator), vital signs, weight, physical examination, clinical laboratory tests (hematology, chemistry, and urinalysis), and urine pregnancy test (females of childbearing potential only) will be conducted according to the schedule for each visit during Treatment Period. Efficacy assessments including PDQ-39, MDS-UPDRS Part 3 and Part 4, KPPS, and MMSE will be conducted at Visit 4 (EOT). Subjects will complete the diary for at least 3 consecutive days prior to Visit 4 (EOT), and the investigators will review the completed diary together with subjects at Visit 4 (EOT).

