### 9.3.1 Inclusion Criteria

To be eligible for inclusion into this trial, the subjects must fulfill all of the following criteria:

1. Male or female, age  $\geq 19$  years at the time of informed consent
2. Patients who meet the clinical diagnostic criteria of Movement Disorder Society (MDS) diagnostic criteria 2015 for Parkinson's disease, have motor fluctuations with  $\geq 1.5$  hours of "off" time throughout the day which is confirmed at the time of Screening and take levodopa 3 or more times a day
3. Parkinson's Disease patients who are receiving levodopa without COMT inhibitor and/or MAO-B inhibitor

CCI

4. Be able to maintain an accurate and complete diary with the help of a caregiver as needed, recording "on" time, "on" time with dyskinesia, "off" time, and time asleep
5. Be able to provide written informed consent
6. Patients whose cognitive function, at the discretion of an investigator, is at a level appropriate to participate in the clinical trial (i.e., with a GDS score of 3 or less or a CDR of 0.5 or less within 3 months prior to Screening)

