### 9.3.2 Exclusion Criteria

To be eligible for inclusion into this trial, the subjects must not meet any of the following criteria:

1. Females who are planning for pregnancy, pregnant or breastfeeding
2. Prior use of safinamide
3. If patients have previously taken medication such as COMT inhibitor and/or MAO-B inhibitor, they have to take appropriate wash-out period for each medication.(3 days for COMT inhibitor; 14 days for MAO-B inhibitor)
4. Use of medications for depression or psychosis within 5 weeks prior to Screening Visit
5. History of allergic response to levodopa, or other anti-Parkinsonian agent
6. Hypersensitivity or contraindications to MAO-B inhibitors
7. Confirmed ophthalmologic history including any of the following conditions: albino subjects, family history of hereditary retinal disease, progressive and/or severe diminution of visual acuity (i.e., 20/70 on Snellen Chart), retinitis pigmentosa, retinal pigmentation due to any cause, any active retinopathy or ocular inflammation (uveitis), or diabetic retinopathy.
8. Patients who did not consent to having at least 7 days of washout period prior to Visit 2, if known to take narcotic analgesics 7 days prior to Screening Visit (eg, pethidine hydrochloride-containing products, tramadol hydrochloride, or tapentadol hydrochloride)
9. History of serotonergic medications administration (eg, tricyclic antidepressants, tetracyclic antidepressants, selective serotonin reuptake inhibitors, serotonin–noradrenaline reuptake inhibitors, selective noradrenaline reuptake inhibitor, or noradrenergic and serotonergic antidepressant) within 5 weeks prior to the Screening Visit
10. Administering central nervous system stimulants (eg, methylphenidate hydrochloride, lisdexamfetamine mesilate)
11. Administering dextromethorphan
12. Patients with clinically significant liver function abnormalities defined as > 1.5 times of the upper limit of the normal range of total bilirubin or > 3 times of the upper limit of the normal range of ALT or AST; re-examination and re-screening are allowed once within the screening period
13. Have a history of hypersensitivity to any of the ingredients of the product
14. Currently enrolled in another clinical trial or used any investigational drug/biologics or device within 30 days or 5 × the half-life, whichever is longer, preceding informed consent

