#### **9.5.1.2.1 Subject Diary**

Information on daily “off” time and “on” time will be collected by subject diary. Subjects and/or their caregivers will receive a subject diary, and investigator will train them how to complete the diary at Visit 1 (Screening).

Subjects will complete the diary for at least 3 consecutive days prior to each visit where completed diary review is conducted (Visit 2, Visit 4) and the diary will be maintained by the subject over a 24-hour period each day the diary is being completed. At 30-minute intervals throughout the period, the subject/caregiver will record whether the subject is currently 1) in an “on” phase, 2) in an “on” phase with dyskinesia, 3) in an “off” phase, or 4) asleep. Subjects will also check when they take their levodopa throughout the day.

An “off” phase will be defined as lack of mobility, bradykinesia, or akinesia whereas in an “on” phase, the subject will be functioning as well as can be expected for that subject, irrespective of whether or not he/she is having dyskinesia.

The daily “off” time is defined as the mean of the total daily “off” time during the last two 24-hour diary recording periods prior to the visit. The daily “on” time is defined as the mean of the total daily “on” time during the last two 24-hour diary recording periods prior to the visit.

Investigators will review the completed subject diary with subjects at Visit 2 (Baseline) and Visit 4 (EOT) and record the results of the subject diary in CRF. At Visit 4 (EOT), subjects will submit the subject diary to clinical trial staff or investigators.

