#### **9.5.1.2.4 MDS-UPDRS Part 4**

In MDS-UPDRS Part 4, raters use historical and objective information to assess two motor complications, dyskinesias and motor fluctuations that include OFF-state dystonia. Raters will use all information from patient, caregiver, and the examination to answer the six questions that summarize function over the past week including today. This section has instructions for the raters and also instructions to be read to the patient, and integrates patient-derived information with the rater's clinical observations and judgments. In Part A, the duration of, disability caused by, and functional impact of any dyskinesias experienced by the subject are rated on a scale from 0 to 4. Clinical fluctuations are assessed in Part B, which includes time spent in "off" state (estimation of the proportion of the waking day spent in the "off" state), functional impact of fluctuations, the predictability and timing of the subject's "off" periods, and proportion of the "off" state having painful dystonia.

After completing MDS-UPDRS Part 4, the investigators will record the result in CRF.

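### Does the off-time analysis need an added sensitivity analysis because the scored baseline diary days can fall inside a COMT-inhibitor wash-out?

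*Combined protocol and SAP*

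**What the plan says.** Section 9.1 fixes the wash-out to the baseline visit: "they have to undergo an appropriate wash-out period for each medication before conducting Visit 2 (Baseline"). Section 9.1.1 gives its length as "3 days for COMT inhibitor; 14 days for MAO-B inhibitor".

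Section 9.5.1.2.1 asks for a diary on at least three consecutive days before Visit 2 and defines daily off time as the mean of the daily totals "during the last two 24-hour diary recording periods prior to the visit".

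Four places bear on the order of wash-out and diary:

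- Section 9.1.1, on who is told to keep the diary: "Subjects who meet the eligibility criteria of the study will be instructed to complete the diary for 3 consecutive days".
- Section 9.3.1, criterion 3, admits patients "who are receiving levodopa without COMT inhibitor and/or MAO-B inhibitor".
- Section 9.3.2, criterion 3, makes wash-out an eligibility item: "they have to take appropriate wash-out period for each medication".
- Section 9.1.3, on entry to treatment: "Subjects whose screening assessments including the wash-out period and evaluations are completed and reviewed by the investigators".

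The primary analysis (9.7.1.7.1) is a paired t-test on the change at week 18. Section 9.7.1.7 uses the FAS first and the PPS second. Section 9.7.1.9 names levodopa dose as the only subgroup. Further detail, including the PPS criteria, is left to a separate SAP.

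**The concern.** Section 7.1 says that COMT and MAO-B inhibitors usually improve wearing-off, so stopping one shortly before baseline could plausibly alter baseline off time. A residual effect of the old drug would make baseline look better than the settled state on levodopa alone. A temporary worsening after withdrawal would make it look worse. COMT inhibitors stay prohibited during the trial (9.4.7.2), so the week-18 value is taken long after stopping, while baseline may be taken in transition.

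With one arm and no adjustment, a shift of this kind cannot be separated from the effect of safinamide. At stake is the size and meaning of the off-time estimate. The natural request is a supportive estimate that leaves out subjects whose scored days overlap a wash-out, so that readers can see whether the result depends on them.

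**Working it through.** **Inputs.** From the documents: wash-out of 3 days (COMT) and 14 days (MAO-B); at least 3 diary days, the last 2 scored; screening of at most 21 days; planned off-time change −1.56 h, SD 2.35 h; PDQ-39 change −3.17, SD 10.86; two-sided 2.5% level; 149 evaluable subjects, 199 enrolled. Assumed, because the documents are silent: affected share f = 10% to 40%; a baseline shift of 1 h, either sign, in those subjects; the planned SD in both groups.

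**The plan's own figures.** The exact paired t-test at two-sided 0.025 gives n = 31 for off time (power 0.903) and n = 149 for PDQ-39 (power 0.902). 149/0.75 = 198.7, rounded up to 199. All agree with section 9.7.2.

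**Day count.** Let Visit 2 be day 0 and take the latest permitted timing.

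- COMT inhibitor: last dose day −4; wash-out days −3 to −1; diary days −3 to −1; scored days −2 and −1. Both scored days are wash-out days and neither is an on-drug day.
- MAO-B inhibitor: the scored days are days 13 and 14 of 14, so the overlap is nominal.
- PDQ-39 is completed at Visit 2, after wash-out. The documents state no recall period, so no overlap can be shown.
- MDS-UPDRS Part 4 uses "six questions that summarize function over the past week including today", which is days −6 to 0. Days −6, −5 and −4 can be on the COMT inhibitor, 3 of 7. This touches a secondary endpoint only.

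Wash-out followed by a full diary takes 3 + 3 = 6 days or 14 + 3 = 17 days. Both fit in the 21-day screening period, so nothing forces the overlap.

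**Effect on the result.** The overall change moves by f × 1 h = 0.10 to 0.40 h. Divided by 1.56 h, that is 6.4% to 25.6%.

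**Precision of an estimate without these subjects.** The half-width is t(0.9875, n−1) × 2.35/√n. At n = 149 it is 2.264 × 2.35/12.21 = 0.436 h. At n = 89 it is 2.280 × 2.35/9.434 = 0.568 h, with power above 99.9% for 1.56 h.

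**Can that estimate show the influence?** The quantity of interest is the overall mean minus the restricted mean, which equals f times the difference between the two groups. Its half-width is t(0.9875, 147) × 2.35 × √(1/n₀ − 1/149), where n₀ is the number kept and t = 2.265.

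| Left out / kept | Movement from a 1 h shift | Half-width of overall minus restricted | Power to detect a 1 h shift |
|---|---|---|---|
| 15 / 134 | 0.10 h | 0.146 h | 24% |
| 30 / 119 | 0.20 h | 0.219 h | 43% |
| 45 / 104 | 0.30 h | 0.287 h | 55% |
| 60 / 89 | 0.40 h | 0.358 h | 61% |

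The movement is smaller than its half-width in the first two rows and only slightly larger in the last two.

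**The case for a change.** The strongest case for acting is that the order is left open. The only dated anchor is Visit 2, eligibility is reconfirmed there (9.5.2.2.2), and section 9.1.3 requires the wash-out to be complete before treatment, not before the diary. A site could follow every word and still score both days inside the wash-out. If safinamide had no effect and a bias in its favour were present, the chance of a significant off-time result at n = 149 would rise from 2.5% to 4.5% at 0.10 h, 11.3% at 0.20 h and 24.3% at 0.30 h. The remedy looks cheap, since medication stop dates are collected (9.4.7) and the SAP is to be finalised before database lock.

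The silence on order stands, and so does the arithmetic. The inference to a defect does not. Those error rates need an assumed share, an assumed shift, an assumed direction and a drug with no effect. If the planned 1.56 h effect is real, a 0.30 h bias against the drug leaves power above 99%. The relevant share is also not all former COMT-inhibitor users, only those who stopped close to the minimum time.

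The remedy is weaker than it looks. Wash-out status is not randomised, so former users may differ in other ways, and a difference could not be put down to diary timing. Excluding MAO-B subjects or splitting PDQ-39 would answer overlaps that are nominal or not shown. Flagging subjects also needs diary dates by day, and section 9.5.1.2.1 says only that diary results go into the CRF.

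**Conclusion.** No change to the plan is called for. The protocol leaves open whether wash-out must end before the scored diary days. Giving the diary instruction to eligible subjects, with wash-out itself an eligibility item, makes wash-out first a fair reading, and the screening period leaves room for it. At the tightest timing both scored days are COMT wash-out days, but none is on drug. If the state after stopping is stable, the change from that baseline is a valid estimate for the population of inclusion criterion 3.

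The possible influence is 0.10 to 0.40 h per hour of shift, 6% to 26% of 1.56 h, resting wholly on an assumed 10% to 40% affected. The documents do not show that any shift exists. The extra analysis would leave the primary result as it is and has 24% to 61% power to detect a 1 h shift. It is an optional descriptive table, not a correction. The Part 4 recall overlap is real at minimum timing but concerns a secondary scale.

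This conclusion rests on the visible text. The separate SAP and the redacted text after inclusion criterion 3 and in section 9.4.7 were not available and may already settle the order.
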